9.1 Standardized methods

Standardized photographs and clinician grading scales will be obtained at baseline and follow-up visits. Camera angle, distance and lighting conditions will be controlled to insure consistency for before and after photographs.

Primary Outcome Measures:

The primary outcome measures that will be analyzed include qualitative clinician grading assessment of improvement as well as patient self-assessed satisfaction. Secondary measures may include colorimeter measurements of changes in skin color and/or other instruments to measure skin properties or visualize the skin using an ultrasound device.

10 Risks and Benefits

10.1 Potential Risks

There is a risk of adverse events, skin reactions or side effects. Expected side effects include:

- Discomfort. Mild discomfort is typical during the treatment of benign pigmented lesions. For tattoo removal treatments, where higher settings are typically used, moderate to significant discomfort is frequently reported. Most patients describe the discomfort as less than when the tattoo was applied. Some areas are more sensitive than others.
- Edema and erythema. Swelling and redness often occur, but will subside in 2-5 days and can be reduced with regular ice application.
- Purpura. The area may appear to be bruised after treatment. The bruising will typically fade in 5-7 days.
- Texture changes. Transient texture changes are often noted, but usually resolve with time. Blisters/scabs/crusting. These may occur and usually take 4-10 days to heal and up to 2 weeks for off-face treatments.
- Petechia or pinpoint bleeding. For tattoo removal treatments, pinpoint bleeding or

- oozing may develop and can continue up to 2 days post-treatment. Pinpoint bleeding is less common during treatment of benign pigmented lesions but may develop and will typically resolve within a few hours post-treatment.
- Hyper/hypopigmentation. Skin can develop temporary lightening or darkening after laser treatment. Hyperpigmentation can be worsened with sun exposure. Hypopigmentation usually occurs after multiple treatments. Pigmentary issues typically resolve with time, but can be permanent.
 - Allergic reaction. Patients who have had a prior allergic reaction to ink during tattoo application may have a similar reaction after laser treatment. This reaction can be controlled by a pre-treatment and/or post-treatment regimen of steroids and antihistamines.
 - Infection. Despite good wound care, pain, swelling, oozing, and fever can indicate the development of an infection. Topical and/or oral antibiotics may be necessary.
 - Scarring. Scarring is a rare occurrence, but it is a possibility if the skin's surface is disrupted. To minimize the chances of scarring, it is important that patients follow all post-treatment instructions provided by their healthcare provider. Good post-treatment care can help reduce the possibility of scarring.
 - Darkening of lesions. Lesions will darken post-treatment and will slough 5-21 days post-treatment.
 - Paradoxical darkening or color change. Some tattoo inks, including many lighter and skin-tone inks, may darken or change color in response to treatment.
 - “Bleeding” of ink into surrounding skin. May result in smudging or loss of definition of a tattoo rather than removal.

10.2 Potential Benefits

Subjects who participate in this study may benefit from an aesthetic improvement in the reduction of the appearance of their tattoo or benign pigmented lesions. There are, however, no guarantees of these or any other benefits from participation. Multiple treatments for removal of pigmented lesions are common, and complete clearing is not always possible. Multiple treatments are required for tattoo removal, and complete clearing is not always possible. Not all ink colors and compositions will respond to tattoo removal treatment.

11 Adverse Events

Adverse events (AE) and/or Unanticipated Adverse Device Effects (UADE) that occur during the course of the study will be documented in the subject's study records and reported to the Sponsor and IRB as required.

Serious Adverse Events (SAE) will be reported by the Investigator to the Sponsor and IRB immediately upon learning of the event.

Unanticipated Adverse Device Effect (UADE) will be reported as soon as possible to the Sponsor and IRB, but no later than 10 working days after first learning of the effect. The Sponsor requests, however, notification within 48 hours after learning of any UADE.

Severity

Severity of adverse events will be scored by the Investigator or his/her designee using the following scale:

- | | |
|-------------------|---|
| 0=None | No adverse event observed |
| 1=Trace | Slightly observable sign or symptom of adverse event |
| 2=Mild | Minimal sign or symptom, usually transient which resolves in a week, which requires no special medical intervention |
| 3=Moderate | Sign or symptom sometimes lasting more than a week, which may require simple medical intervention |
| 4=Severe | Sign or symptom that is intense or debilitating, sometimes lasting several weeks or longer; requires medical intervention |

Relationship to Treatment

The relationship between an adverse event (AE) and treatment is defined as follows:

- | | |
|-----------------------------|---|
| Related | An adverse event that appears in the treatment area and has a direct relationship to the study treatment administered, and such that another etiology is highly unlikely |
| Probably Related | An adverse event that appears in the treatment area that has a strong temporal relationship to the study treatment, and such that another etiology is unlikely or significantly less likely |
| Possibly Related | An adverse event that appears in the treatment area that has a strong temporal relationship to the treatment, and such that another etiology is equally possible |
| Probably Not Related | An adverse event that appears in the treatment area that has little to no temporal relationship to the study treatment, and such that another etiology is likely to exist |
| Not Related | An adverse event that appears in the treatment area that has no temporal relationship to the study treatment, and such that another etiology is nearly certain |

12 Subject Accountability

Study participation is voluntary and subjects may withdraw from the study at any time for any reason. In case of subject withdrawal, additional subjects may be enrolled into the study as replacements with prior approval from Sponsor and IRB.

13 Records and Reporting

It is the responsibility of each Investigator to report all AE, SAE and UADE to the Sponsor and IRB. SAE will be reported to the Sponsor and IRB immediately. All UADE will be reported to the IRB and FDA as soon as possible, but no later than 10 working days after learning of the effect. The Investigator will include a listing and description of all adverse events as part of the annual progress report.

14 Confidentiality

Subject confidentiality will be met in accordance with the Health Insurance Portability and Accountability Act (HIPAA) and 21CFR Part 50, Protection of Human Rights. These regulations will be followed specifically with regard to the privacy and confidentiality of subject care and study records.

Personnel associated with Investigator's office, along with the Sponsor of this study, Lutronic, Inc., the FDA and the reviewing IRB, have the right to review all of the data, including photographs, collected during this study. These entities are also required to maintain confidentiality.

15 Subject Payment

Subjects will receive \$50 for follow-up visits that occur between treatments and \$100 for the follow-up observations after the last treatment visit. Study treatments and post-treatment care visits will be provided at no cost to the subjects. If subjects have any biopsies done, they will be paid an additional \$150 for participating in the study.

16 References

1. Lee GSC, S. B.; Calderhead, R. G. The single-system answer to multiple applications in the removal of pigmented lesions and tattoos: Lutronic Corp; 2016. 8 p.

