6.5 Study Treatment

Selection of settings will be based upon the practitioner's judgement and in accordance with treatment guidelines, publications and experience with similar ultrashort pulse laser devices. A series of test spots may be performed within the treatment area or on a less noticeable area with similar skin color and texture. After application of test spots, skin reactions will develop and can be evaluated for selection of setting parameters usually in 15 minutes for Skin Types I – III, but will take from 24 – 72hrs or longer to develop for darker skin types. For darker skin type subjects, if test spots are used to establish treatment settings, the treatment will take place on a separately scheduled session. To help evaluate performance the investigator may compare effects of the PicoPlus laser system to other FDA approved commercially available nanosecond or picosecond laser systems. Commercially available products will be used according to the manufacturer's recommendations and investigator's experience.

In preparation for treatment, the test spot or skin treatment area will be cleansed with mild soap and water and dried. If hair is present, the area should be shaved. Topical anesthetic cream such as BLT will be applied using an occlusive dressing technique for sufficient time (typically 45-60 min) to the point where adequate anesthesia is achieved. If topical anesthetic is used, the anesthetic will be thoroughly removed, the skin wiped clean and then sanitized with an antiseptic scrub such as Hibiclens®. If discomfort is experienced during treatment, subjects may be offered adjunctive cooling such as cold air, cool gel packs, or cold moist cloths. Subject discomfort during study treatment will be documented using a 0 (None) to 10 (Severe) pain rating scale. Mild discomfort is typical during the treatment of benign pigmented lesions. For tattoo removal treatments, because settings are typically higher, moderate to significant discomfort is frequently reported. Most patients describe the discomfort as less than when the tattoo was applied. Some areas are more sensitive than others. Subjects may request that treatment be discontinued at any time for any reason.

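### All five causality definitions, including Not Related, require the event to lie in the treatment area, so off-area and systemic events have no valid code

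*Protocol*

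**What the plan says.** Protocol Section 11, under Relationship to Treatment, presents five categories as the definition of the link between an adverse event and treatment. There is no further category for events that fit none of them. The scale runs from Related, "An adverse event that appears in the treatment area and has a direct relationship to the study treatment administered", to Not Related, "An adverse event that appears in the treatment area that has no temporal relationship to the study treatment". The three categories between them open with the same restriction on location.

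The collection rules carry no such restriction. Section 11 covers adverse events "that occur during the course of the study will be documented", and Section 13 states: "It is the responsibility of each Investigator to report all AE, SAE and UADE to the Sponsor and IRB".

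Section 6.5 describes where the laser may be applied before full treatment: "A series of test spots may be performed within the treatment area or on a less noticeable area with similar skin color and texture". For darker skin types it adds that "if test spots are used to establish treatment settings, the treatment will take place on a separately scheduled session".

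**The concern.** The set of events that must be reported is wider than the set that the causality scale can classify. Two kinds of event fall in the gap.

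- **Off-area test spots.** The laser is fired at skin that Section 6.5 places outside the treatment area. A burn, blister or pigment change there is a device effect, yet the related categories exclude it by location.
- **Events elsewhere in the body or systemic events.** These are the usual examples of unrelated events, but the Not Related definition excludes them too.

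There is a second ambiguity. Section 6.5 speaks of test spots and then of the treatment as something that happens later, in its own session. It is therefore unclear whether the term study treatment in the definitions covers test spots at all.

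This is a multicenter study (Section 5.2). Without a valid code, one site may force the event into the nearest category and another may leave the field blank. The tabulation of device-related events would then depend partly on site habit.

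**Working it through.** No arithmetic beyond counting applies, so the texts are set side by side.

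**1. The relationship scale (Section 11), broken into its conditions**

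| Category | Event must be in treatment area | Link to treatment | Other cause |
|---|---|---|---|
| Related | Yes | Direct | Highly unlikely |
| Probably Related | Yes | Strong, in time | Unlikely or much less likely |
| Possibly Related | Yes | Strong, in time | Equally possible |
| Probably Not Related | Yes | Little or none, in time | Likely |
| Not Related | Yes | None, in time | Nearly certain |

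The wording of the second and third rows confirms the pattern: "An adverse event that appears in the treatment area that has a strong temporal relationship to the study treatment" and "An adverse event that appears in the treatment area that has a strong temporal relationship to the treatment". Definitions with the location condition: 5 of 5. Definitions open to an event elsewhere: 5 − 5 = 0.

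**2. The severity scale (Section 11).** It has five grades, 0 to 4, and none mentions location (0 of 5). The four grades for an observed event, 1 to 4, can be used for any event. An off-area event can therefore be graded for severity but not classified for causality.

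**3. Does the Protocol foresee such events?**

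- Section 6.5 allows test spots in the treatment area or, as an alternative, on other skin. Its paragraph on skin preparation again names the test spot and the treatment area as alternatives. It also says that reactions in darker skin may take 24 to 72 hours or longer to appear.
- Section 10.1 lists fever among the signs of infection.
- Section 6.3 acknowledges side effects of the optional oral analgesic or anxiolytic medication.

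**4. Three test cases, taking the definitions as written**

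| Event | Related categories | Not-related categories |
|---|---|---|
| Laser injury at an off-area test spot | Excluded by location | Excluded by location, and wrong in substance |
| Systemic effect with a plausible link to a study procedure | Excluded by location | Excluded by location |
| Unrelated illness elsewhere in the body | Do not apply | Excluded by location, though the other conditions fit |

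No category accepts any of the three.

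**The case against.** The strongest reply has four parts.

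- **Treatment area is never defined.** Test spots are described under the heading Study Treatment, so an investigator could regard any lasered skin as treated skin. Off-area test spots are also optional. It is true that the term is undefined, but Section 6.5 twice sets the test spot or its site against the treatment area, so this reading goes against the text. It also does nothing for a systemic event.
- **Sites will use common sense.** An unrelated illness would very likely be coded Not Related, because the timing and etiology conditions fit. That is probable, but it means departing from the written definition, and sites get no guidance on the harder case of a test-spot injury.
- **Little depends on the scale.** The outcomes in Section 9 do not use relatedness, and reporting of serious events and unanticipated device effects runs separately from these categories. This stands, and it limits the consequence to the classification of causality.
- **For a locally applied laser, location is real evidence on causality.** This also stands, but evidence is different from an entry condition. Once the condition is gone, location can still inform the judgement of a direct link and of other causes.

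A statistical analysis plan, which is not at hand, would not normally repair this. It would tabulate the codes that investigators assign, and the Protocol is what fixes those codes.

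**Conclusion.** The concern holds. The causality scale excludes every event outside the treatment area, in 5 of 5 definitions, while the Protocol requires such events to be reported and itself allows the laser to be used outside that area. This is a wrongly drawn rule, not a detail left for later.

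For systemic and remote events the conclusion needs no assumption beyond the text. For off-area test spots it rests on the distinction that Section 6.5 draws between test spots and the treatment area.

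The practical effect is modest. Capture, severity grading and expedited reporting are intact, and the number of events affected cannot be estimated from the Protocol. The wording should still be corrected, because it bears on how device-related harm is counted.

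**What to change.** 1. In Section 11, delete the location clause from all five relationship definitions. The sentences remain grammatical, and causality then rests on the link to treatment and on other possible causes.
2. Add one sentence stating that study treatment, for the purpose of these definitions, includes laser test spots wherever they are placed.
3. Record event location as a separate item (treated area, test spot, elsewhere or systemic), if the case report form, which is not shown, does not already do so. This keeps the information that the clause was carrying.

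A narrower alternative would remove the clause from the two not-related categories only and add explicit wording for test spots and other off-area events. It closes the same gap but needs more text.

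The cost is one clause struck from five definitions and one added sentence, plus a data field if none exists. The count of events coded as related may rise, because off-area device effects become classifiable; by how much cannot be said from the Protocol. No treatment or reporting procedure changes.

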18.1 Investigator's Global Assessment of Improvement

At 6 to 12 weeks (24 weeks optional for tattoo removal) post-final treatment as applicable, the Investigator will be asked to rate the degree of tattoo clearing or reduction in benign pigmentation observed in the subject's treated area using the Physician's Global Assessment of Improvement Scale:

- 3 = Very Significant or Complete Clearing (75 – 100%)
- 2 = Significant Clearing (50 – 74%)
- 1 = Moderate Clearing (25 – 49%)
- 0 = Mild or No Clearing (0 – 24%)

18.2 Subject's Global Assessment of Improvement

Subjects will be asked to rate the degree of tattoo clearing or reduction in benign pigmentation at 6 weeks to 12 weeks (24 weeks optional for tattoo removal) post-final treatment as applicable, as compared to baseline, using the Subject's Global Assessment of Improvement Scale:

- 3 = Very Significant or Complete Clearing (75 – 100%)
- 2 = Significant Clearing (50 – 74%)
- 1 = Moderate Clearing (25 – 49%)
- 0 = Mild or No Clearing (0 – 24%)

18.3 Subject Satisfaction Assessment

At 6 weeks to 12 weeks (24 weeks optional for tattoo removal) post-final treatment as applicable, subjects will be asked to rate their level of satisfaction with the laser treatment outcome and the overall laser treatment procedure, using the Subject Satisfaction Assessment Scale:

- 2 = Extremely Satisfied
- 1 = Satisfied
- 0 = Neutral
- 1 = Unsatisfied
- 2 = Extremely Unsatisfied

18.4 Blinded Reviewer's Global Assessment of Improvement

At 6 weeks to 12 weeks (24 weeks optional for tattoo removal) post-final treatment, the blinded reviewers may be asked to perform an assessment of subject photographs. Each reviewer will be asked to first determine the temporal order (before and after) of each photograph pair, and then rate the degree of tattoo clearing or reduction in benign pigmentation observed in the post-treatment photograph using the Global Assessment of Improvement Scale:

- 3 = Very Significant or Complete Clearing (75 – 100%)
- 2 = Significant Clearing (50 – 74%)
- 1 = Moderate Clearing (25 – 49%)
- 0 = Mild or No Clearing (0 – 24%)

18.5 Melasma Area Severity Index (MASI)

At 6 – 12 weeks (24 weeks optional) post-final treatment for melasma, blinded graders will use the melasma area severity index (16) to grade the baseline and after photos. The severity of the melasma in each of the four regions (forehead, right malar region, left malar region and chin) is assessed based on three variables: percentage of the total area involved (A), darkness (D), and homogeneity (H).

A numerical value assigned for the corresponding percentage area involved is as follows: 0=no involvement; 1=<10% involvement; 2=10-29% involvement; 3=30-49% involvement; 4=50-69% involvement; 5=70-89% involvement; and 6=90-100% involvement. The darkness of the melasma (D) is compared to the normal skin and graded on a scale of 0 to 4 as follows: 0=normal skin color without evidence of hyperpigmentation; 1=barely visible hyperpigmentation; 2=mild hyperpigmentation; 3=moderate hyperpigmentation; 4=severe hyperpigmentation. Homogeneity of the hyperpigmentation (H) is also graded on a scale of 0 to 4 as follows: 0=normal skin color without evidence of hyperpigmentation; 1=specks of involvement; 2=small patchy areas of involvement <1.5 cm diameter; 3=patches of involvement >2 cm diameter; 4=uniform skin involvement without any clear areas).

To calculate the MASI score, the sum of the severity grade for darkness (D) and homogeneity (H) is multiplied by the numerical value of the areas (A) involved and by the percentages of the four facial areas (10-30%).

Total MASI score: Forehead 0.3 (D+H)A + right malar 0.3 (D+H)A + left malar 0.3 (D+H)A + chin 0.1 (D+H)A

[figure not shown]

Fig 1. The Melasma Area and Severity Index (MASI).⁸ Published with permission. Topical retinoic acid (tretinoin) for melasma in black patients. Arch Dermatol © 1994; 130: 727–33. American Medical Association. All rights reserved.
